5.2.4. Standard derivations and reporting conventions

The following conversion factors will be used to convert days into weeks, months or years: 1 week = 7 days, 1 month = 30.4375 days, 1 year = 365.25 days.

Demographics and physical measurements:

- Age [years]:
 - (date of given informed consent date of birth + 1) / 365.25
 - In case of missing day, day only: Age [years]: (year/month of given informed consent year/month of birth)
 - In case only year of birth is given: Age [years]: (year of given informed consent year of birth)

The integer part of the calculated age will be used for reporting purposes.

• BMI (kg/m^2) = weight $(kg)/[height (m)]^2$

For reporting conventions, mean and median should generally be displayed one more decimal place than the raw data and standard deviation should be displayed to two more decimal places than the raw data. Percentages will be reported to one decimal place. The

rounding will be performed to closest integer / first decimal using the common mid-point between the two consecutive values. E.g., 3.1 to 3.4 will be rounded to an integer of 3, and 3.5 to 3.9 will be rounded to an integer of 4.

5.2.5. Unscheduled visits

Subjects may return to the site for unscheduled visits in the event of an AE, SAE or as deemed necessary by the Investigator. The same procedures as per any other post-Baseline Visits may be conducted. Data collected will be reported in the 'Unscheduled Visit' eCRF page.

Data from unscheduled visits will be summarized by assigning to closest visit within a 6-week window. If two unscheduled visits occur in a row the last one will be assigned (Last Observation Carried Forward approach).

All unscheduled visits info will be listed, flagging those that have been assigned to a prescheduled visit.

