2.2. Study Design

This is a multicenter, open label extension study evaluating the safety of Patidegib Topical Gel, 2%, applied topically twice daily to the face of adult subjects with Gorlin syndrome. The treatment duration is 12 months, with potential extension beyond this period.

All study participants will be treated with Patidegib Topical Gel 2%.

A Screening visit will be mandatory for all subjects, with the possibility for rescreening for those who fail screen. Subjects will need to meet all I/E criteria at screening/rescreening visit. Completers from study Pelle-926-301 will have their Screening visit after the Study Pelle-926-301 End of treatment visit.

Study visits will occur at quarterly intervals. However for WOCBP, study visits will occur monthly. For the first application, the subject will apply the IP to the face at the study site under the direction of the Study Coordinator (or designee). The IP should be applied after all clinical assessments. Patients will be dispensed a diary to maintain a log of their IP application.

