3.4. Baseline Variables

3.4.1. Study drug, study treatment and baseline definitions

In this study, either 'study drug', 'study treatment' or 'Investigational product (IP)' refer to Patidegib Topical Gel, 2%.

Start and end dates of study treatment:

The date/time of first dose of study treatment is the earliest date/time of non-zero dosing of the study drug.

The date/time of last dose of study treatment is the latest date/time of non-zero dosing of the study drug.

Definition of baseline:

In this study, baseline value will refer to the last assessment prior to the first dose.

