5.2.3. Definition of on-treatment period

Safety endpoints will be summarized based on the on-treatment period unless otherwise specified.

On-treatment period is defined as the time from the first IP application of study treatment to last IP application of study treatment + 30 days.

Safety data collected outside the on-treatment period as well as data from unscheduled visits will be listed and flagged in listings but not summarized.

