6.2.2. Efficacy endpoints

The efficacy endpoints are:

- 1. The number of facial BCCs removed by surgery (per Investigator determination) and histologically verified as BCC; from Baseline to Month 12.
- 2. The number of facial BCCs removed by surgery (per Investigator determination) and histologically verified as BCC; from Baseline to Month 6.
- 3. The number of facial BCCs removed by surgery (per Investigator determination) from Baseline to Month 12.
- 4. The number of facial BCCs removed by surgery (per Investigator determination) from Baseline to Month 6.
- 5. Change from Baseline to Month 12 in the total number of facial lesions suspicious for BCC.

- 6. Count of facial lesions suspicious for BCC over time.
- 7. aBCCdex change in lesion score from Baseline to Month 12.

All efficacy assessments will be summarized descriptively by visit, depending on the nature of the variable. Changes from Baseline will also be displayed.

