6.4.2. Adverse Events

AEs will be graded by the investigator and coded using most recent version of the Medical Dictionary for Regulatory Activities (MedDRA).

Treatment-emergent adverse events (TEAEs) are those events with onset dates occurring during the on-treatment period for the first time, or if the worsening of an event is during the on-treatment period.

All analyses described **Error! Reference source not found.** will be based on TEAEs (started during the on-treatment period) if not otherwise specified. The AE listings will include all AEs (whether treatment-emergent or not). AEs outside the on-treatment period will be flagged in the listings.

- Related Adverse Events: adverse events with relationship to study treatment (as recorded on the AE eCRF page, Relationship with study treatment = Possibly / Probably / Definitely) reported by the investigator and those of unknown relationship (i.e., no answer to the question 'Relationship with study treatment'). Related AEs are those related to any study treatment.
- **Serious Adverse Events (SAE):** serious adverse events (as recorded on the AE eCRF page, Serious Adverse Event = Yes).
- Adverse Events Leading to Permanent Treatment Discontinuation: adverse events leading to permanent discontinuation of study treatment (as recorded on the AE eCRF page, Action taken with study treatment = Drug withdrawn).

• Adverse Events Leading to Death: adverse event leading to death (as recorded on the AE eCRF page, Outcome = Fatal).

Unless otherwise specified, AEs will be summarized by number and percentage of patients with the AE in the category of interest as described above, by primary SOC and PT in decreasing frequency based on the frequencies observed.

Each patient will be counted only once within each SOC or PT. If a patient experiences more than one AE within a SOC or PT for the same summary period, only the AE with the strongest relationship or the worst severity, as appropriate, will be included in the summaries of relationship and severity.

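### The unscheduled-visit rule in SAP 5.2.5 can assign post-dose data to the Baseline visit and contradicts SAP 5.2.3

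*SAP*

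**What the plan says.** SAP 5.2.5 gives the assignment rule: "Data from unscheduled visits will be summarized by assigning to closest visit within a 6-week window". For consecutive unscheduled visits it adds: "If two unscheduled visits occur in a row the last one will be assigned (Last Observation Carried Forward approach"). It does not name the visits that can be targets, does not say whether six weeks is a half-width or the full width, and does not say what happens when the target visit already has a scheduled value.

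Two other SAP sections bear on the same records.

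- SAP 3.4.1 defines baseline: "In this study, baseline value will refer to the last assessment prior to the first dose".
- SAP 5.2.3, on the on-treatment period, says: "Safety data collected outside the on-treatment period as well as data from unscheduled visits will be listed and flagged in listings but not summarized".

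The outputs exposed to visit assignment are the by-visit ones. SAP 6.2.2 says: "All efficacy assessments will be summarized descriptively by visit, depending on the nature of the variable". SAP 6.4.1 (dermal shift tables) and SAP 6.4.4 (vital signs) are also laid out by visit against baseline.

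**The concern.** Baseline is a scheduled visit on Day 1 (Protocol Table 1), and the next visit with dermal, vital-sign and efficacy assessments is Month 3. A closest-visit rule that leaves Baseline as a candidate sends a record made shortly after the first application back to a pre-dose visit. SAP 3.4.1 says that such a record cannot be the baseline value, so the two rules together leave it without a proper place. It is either displayed in the Baseline row beside pre-dose data or assigned to no row.

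Safety and tolerability are the primary objective, and SAP 6.1.1 names dermal tolerability as one component. Unscheduled visits are prompted by adverse events or by the investigator's judgement, so their findings are more likely than average to be abnormal. The weeks after Baseline are also when subjects who had vehicle in the parent study first use active gel (Protocol section 6).

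SAP 5.2.3 and 5.2.5 also give the programmer opposite instructions: one keeps unscheduled data out of the summaries and the other puts them in.

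**Working it through.** The plan gives no figure to reproduce, so the check maps study days to visits under the stated rule.

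**Inputs**

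- Visit spacing (SAP 2.2): "Study visits will occur at quarterly intervals. However for WOCBP, study visits will occur monthly".
- Conversions (SAP 5.2.4): "1 week = 7 days, 1 month = 30.4375 days, 1 year = 365.25 days".
- First application is Day 1 (SAP 5.2.2).
- Assumption: visits fall on their nominal days.

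**Quarterly schedule**

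- Month 3 = Day 1 + 3 × 30.4375 = Day 1 + 91.3, about Day 92.
- Midpoint between Baseline and Month 3 = Day 1 + 91.3/2 = Day 46.7. Any record up to Day 46 is closer to Baseline.
- Six weeks = 6 × 7 = 42 days.

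| Reading of the window | Assigned to Baseline | Assigned to no visit | First day assigned to Month 3 |
|---|---|---|---|
| ±42 days | Days 2–43 (42 days) | Days 44–50 (7 days) | Day 51 |
| Six weeks in total, ±21 days | Days 2–22 (21 days) | Days 23–71 (49 days) | Day 72 |

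As shares of the interval to Month 3: 42/91.3 = 46% and 21/91.3 = 23%. Under either reading, no record before Day 51 reaches a post-baseline row.

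**Monthly schedule for women of childbearing potential**

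If the monthly visits count as targets, the midpoint to Month 1 is Day 1 + 30.4375/2 = Day 16.2. Days 2–16 then go to Baseline under either reading, and Month 1 begins at Day 17. Table 1 schedules no dermal, efficacy or physical-examination assessment at Months 1 and 2. If targets are limited to visits where the assessment is scheduled, these subjects follow the quarterly result.

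**Which data are exposed**

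- Not exposed: treatment-emergent event tables, which go by onset date (SAP 6.4.2: "Treatment-emergent adverse events (TEAEs) are those events with onset dates occurring during the on-treatment period for the first time"). The serious-event and discontinuation tables are built on the same treatment-emergent events.
- Largely recaptured: pain/burning and pruritus, scored as worst since the last visit (Protocol Table 2), and lesion removals, counted since the last visit (Protocol 8.2). Recapture is incomplete if the unscheduled visit itself counts as the last visit.
- Exposed: erythema, edema, crusting, vital signs and any lesion count taken at the unscheduled visit, all of which are point-in-time.

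Example: moderate erythema at an unscheduled visit on Day 20, on the quarterly schedule, maps to Baseline under both readings. If it has cleared by Month 3 and was not entered as an adverse event, it appears in listings but in no post-baseline by-visit row. If a second unscheduled visit follows with a resolved score, the last-one rule in 5.2.5 also displaces the earlier peak.

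**Would barring Baseline be enough?**

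No. With only post-baseline targets and the same window on the quarterly schedule, Days 2–50 (±42) or Days 2–71 (±21) map to no visit. Baseline is protected, but the early records still have no row.

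**The case against.** The strongest reply is that SAP 3.4.1 already settles the matter. A post-dose record cannot be the last assessment before the first dose, so every change and shift from baseline uses a pre-dose reference. SAP 5.2.5 also likens unscheduled procedures to those of other post-Baseline visits, which suggests that post-baseline targets were intended. This stands as far as the baseline value goes. A reader might infer that a raised early score becomes the reference and makes later visits look like improvement; that would require the program to ignore 3.4.1, and the documents do not support it.

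A reader might also infer that early findings vanish from every post-baseline summary. They do not, given the onset-date and since-last-visit rules. In addition, Protocol 8.3.1 requires a local reaction that needs therapy, or that interrupts or stops the gel, to be reported as a safety event. Protocol 11.1.1 asks more generally for signs and symptoms to be entered as adverse events, so some milder reactions may be caught too. All unscheduled data are listed.

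Finally, if SAP 5.2.3 governs safety data, no unscheduled dermal score or vital sign from any time on study is summarized, and the closest-visit rule is not what removes them. That is correct, but 5.2.5 says the opposite and neither section takes precedence. Lesion counts are efficacy data and would remain under 5.2.5 in any case.

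**Conclusion.** The point holds in a limited form. Read literally, SAP 5.2.5 sends post-dose unscheduled records to a pre-dose visit for the first six weeks (Days 2–43) or three weeks (Days 2–22) on the quarterly schedule, depending on how the window is read. The consequence is a misplaced or missing by-visit row for point-in-time dermal signs, vital signs and lesion counts. The baseline reference is not biased, provided 3.4.1 is applied. The contradiction between 5.2.3 and 5.2.5 is equally important, because it decides whether unscheduled dermal and vital-sign data enter any by-visit summary.

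The 46% and 23% are shares of calendar days, not of data. The documents give no rate of unscheduled visits, so the number of records affected is unknown. A difference in tabulation by fertility status is possible only if monthly visits serve as targets for assessments not scheduled there, which the SAP does not say. The study is single-arm and descriptive, so no test or decision rule is affected. What is at stake is how completely early tolerability is shown.

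**What to change.** 1. Reconcile SAP 5.2.3 and 5.2.5 so that one rule governs unscheduled data, stated for safety and efficacy data alike. Editing 5.2.5 alone would leave dermal scores and vital signs unresolved.
2. State in 5.2.5 that data collected after the first application are assigned only to post-baseline visits at which that assessment is scheduled, are never assigned to Baseline, and never replace a scheduled value.
3. Define the window explicitly as plus or minus a number of days.
4. Show on-treatment records that fall before the Month 3 window in a separate early on-treatment row, or add a worst-post-baseline summary for the dermal scores. Without this, item 2 only moves the early records from Baseline to no visit.

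The cost is a few SAP sentences and one change to the visit-assignment program. No data collection changes.

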5.3. Methods to Manage Missing Data

5.3.1. Missing data

No missing data imputation is planned. All summaries will use observed data only. Missing statistics, e.g. when they cannot be calculated, should be presented as 'ND' or 'NA'.

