7.3 Study Drug Discontinuation

The Investigator has the right to permanently discontinue IP application of a subject at any time if in their opinion the continuation of the IP is deleterious to the subject's health or discontinuation is in the subject's best interest. If the subject becomes pregnant, IP will be discontinued immediately.

If, for any reason, a subject is discontinued during the treatment period prior to the Exit Visit, evaluations should be performed at the time of early termination and the reason for termination should be recorded in the end of study source documentation. At the 30 day follow up additional information may be collected. All data gathered on the subject will be made available to PellePharm.

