8.2 Efficacy Assessments

At the Baseline visit, the number of lesions on the face that are suspicious for BCC will be recorded. Additionally, the number of lesions on the face that are suspicious for BCC and that the patient consents to have removed in accordance with PI recommendation will also be recorded. These will be removed prior to the next Post-baseline quarterly visit.

At all quarterly visits, the number of lesions on the face that are suspicious for BCC will be recorded. Additionally, the number of lesions on the face that were suspicious for BCC and removed since the last visit will be recorded. Finally the number of lesions on the face that were suspicious for BCC, removed and confirmed on histology to be BCC will be recorded.

The count of facial lesions will exclude lesions on the face where IP should not be applied (i.e eyelids). Face is defined as in Section 10.4.

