12.6.2 Efficacy Analyses

All analysis will be descriptively summarized. There will be no hypothesis testing. Additional information, including the handling of missing data will be provided in the SAP.

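### Cumulative facial BCC removal counts have no rule for early leavers and no allowance for follow-up time, so the Month 6 and Month 12 figures can mislead

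*SAP*

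**What the plan says.** Four of the seven efficacy endpoints in SAP 6.2.2 are removal counts over a fixed window. Endpoint 1 is "The number of facial BCCs removed by surgery (per Investigator determination) and histologically verified as BCC; from Baseline to Month 12" and endpoint 2 is "The number of facial BCCs removed by surgery (per Investigator determination) and histologically verified as BCC; from Baseline to Month 6". Endpoints 3 and 4 repeat these without the histology condition. The method given is: "All efficacy assessments will be summarized descriptively by visit, depending on the nature of the variable". No rate and no follow-up denominator is mentioned.

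Removals are collected in increments. At each quarterly visit, "the number of lesions on the face that were suspicious for BCC and removed since the last visit will be recorded" (Protocol 8.2). A 6- or 12-month total therefore has to be built by adding visits.

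For a subject discontinued before the Exit Visit, Protocol 7.3 says "evaluations should be performed at the time of early termination" and then "At the 30 day follow up additional information may be collected". Table 1 marks efficacy assessments at Baseline, Months 3, 6 and 9, and Month 12/Exit, with none in the 30-day column. After withdrawal from the study nothing more is collected (Protocol 7.4).

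On missing data, Protocol 12.6.2 defers: "Additional information, including the handling of missing data will be provided in the SAP". The SAP's answer, in 5.3.1, is: "No missing data imputation is planned. All summaries will use observed data only".

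**The concern.** A count over a fixed window has a clear meaning only for subjects observed over the whole window. For anyone who leaves earlier, the plan leaves two readings open.

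- **Partial total.** The Month 12 column of Table 1 is also the End of treatment/Exit Visit, so an early leaver's running total could be filed there and read as a low 12-month count.
- **No value.** If the early visit is instead mapped to the nearest scheduled visit within six weeks, as SAP 5.2.5 does for unscheduled visits, Month 12 stays empty and the figure describes completers only.

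Two programmers following the SAP could thus produce different figures for the first-listed efficacy endpoint. Neither figure accounts for time observed.

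Two comparisons are exposed. The Month 6 and Month 12 counts will be read against each other although they may describe different subjects or different amounts of follow-up. SAP 4.1 also plans endpoints 1 and 3 by HHI history, and unequal drop-out between those subgroups would appear as a difference in surgery.

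Leavers could plausibly differ from stayers. Inclusion criterion 11 limits treatment of facial BCCs to the study gel, with surgery as the only exception, so a subject wanting other treatment has a reason to leave.

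**Working it through.** The documents give no expected count, removal rate or drop-out rate, so there is no planned figure to reproduce. The check uses assumed values.

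**Inputs**
- Fixed-window counts with no denominator: SAP 6.2.2.
- Observed data only: SAP 5.3.1.
- No scheduled count after early termination: Protocol 7.3 and Table 1.
- Assumed: a share d of subjects leaves, evenly over 12 months (5% to 30%).
- Assumed: each subject's removal rate is constant, and leavers have k times the rate of stayers (0.5 to 2).

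**Formulas**, with a stayer's 12-month count set to 1:
- True mean if all were followed = (1 − d) + dk
- Partial totals kept = (1 − d) + dk/2, since a leaver is observed for half a year on average
- Completers only = 1
- Removals per patient-year = [(1 − d) + dk/2] / (1 − d/2)

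**Worked case, d = 20%, k = 2.** True mean = 0.8 + 0.4 = 1.2. Partial totals = 0.8 + 0.2 = 1.0, so −16.7%. Completers = 1.0, so −16.7%. Rate = 1.0/0.9 = 1.11, so −7.4%.

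**Error against the true 12-month mean**

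| Drop-out d | Rate ratio k | Partial totals | Completers only | Per patient-year |
|---|---|---|---|---|
| 5% | 1 | −2.5% | 0% | 0% |
| 10% | 1 | −5.0% | 0% | 0% |
| 20% | 1 | −10.0% | 0% | 0% |
| 30% | 1 | −15.0% | 0% | 0% |
| 20% | 0.5 | −5.6% | +11.1% | +4.9% |
| 20% | 1.5 | −13.6% | −9.1% | −4.0% |
| 20% | 2 | −16.7% | −16.7% | −7.4% |

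A simulation with 200 subjects, 4 removals a year, overdispersed counts and d = 20% agrees. For k = 1 the true, partial, completer and rate means are 4.00, 3.60, 4.00 and 4.00. For k = 2 they are 4.80, 4.00, 4.00 and 4.45.

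**Month 6 against Month 12, d = 20%, no change in anyone's rate**
- Partial totals, k = 1: the first half is 0.8 × 0.5 + 0.2 × (0.25 + 0.125) = 0.475 and the second is 0.900 − 0.475 = 0.425, an apparent fall of 10.5%.
- Observed subjects at each time, k = 1: no apparent change.
- Observed subjects at each time, k = 2: the Month 6 mean is (0.4 + 0.1)/0.9 = 0.556 and the implied second half is 0.444, an apparent fall of 20%.
- Observed subjects at each time, k = 0.5: the Month 6 mean is (0.4 + 0.025)/0.9 = 0.472 and the implied second half is 0.528, an apparent rise of about 12%.

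**HHI subgroups.** With equal rates and partial totals, 10% drop-out in one subgroup and 30% in the other gives means of 0.95 and 0.85. Since 0.85/0.95 = 0.895, a difference of about 10.5% arises from drop-out alone.

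**15-day window.** Lesions found at the Exit Visit must be removed within 15 days (Table 1 notes). Crediting every leaver with 15 more days changes the 20%, k = 1 shortfall only from 10.0% to 9.2%.

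**The case against.** The study is a single-arm extension with safety as its primary objective. Efficacy is secondary, unpowered and untested, and observed-case reporting is a stated choice. SAP 5.2.1 shows the number missing for continuous variables. SAP 6.3.2.1 tabulates discontinuations with reasons and plots time to treatment discontinuation, so a reader would see denominators shrink. This limits the weight of the point but does not answer it. The number missing does not show whether leavers had more or fewer removals, and if partial totals are kept nobody appears missing. The discontinuation plot is not linked to the counts.

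Some stronger readings are tempting, and the documents do not support them.

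- *Counting stops the day treatment stops.* The early-termination evaluation covers removals to that point, exit lesions may be removed up to 15 days later, and the 30-day visit may add information. What ends is the scheduled recording.
- *Drop-out must show a false fall in surgery.* Completer-only figures are unbiased with equal rates and err upward if leavers have lower rates.
- *The half-year contrast is the only internal comparison.* SAP 4.1 plans HHI subgroups, and endpoints 5 and 6 follow lesion counts from Baseline. No half-year removal contrast is planned; a reader would have to construct it.
- *The distortion is very large.* Suppose 80 subjects have 2 removals per half year, and 20 have 6 and all leave at Month 6. The Month 6 mean is 2.8 and the completer Month 12 mean is 4.0, so the implied second half is 1.2, a 57% fall. That needs every leaver to have three times the others' rate and subtracts means taken over different subjects. Quarterly means in the same example go from 1.4 to 1.0, a 29% fall.

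The first half year is also front-loaded. Lesions chosen for removal at Baseline are taken out before the next quarterly visit (Protocol 8.2), so a later decline could appear without any drop-out. It also means the constant-rate figures overstate the shortfall from partial totals where removals are concentrated early.

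**Conclusion.** The point holds as a defect in how the removal endpoints are summarised. The stated rule permits two figures. One is always too low once leavers would have had further removals. The other is wrong whenever leavers' removal rates differ from stayers', in a direction the plan gives no means of judging.

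The size depends on assumed drop-out and rates. It is trivial at 5% drop-out with equal rates (2.5% low, or no error in completers). At 20% drop-out with a twofold or halved rate in leavers, the completer figure is 16.7% low or 11.1% high.

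This is worth correcting although efficacy is descriptive: with no control arm or test, the displayed count is the result for the secondary objective, and Protocol 6 singles out removal by surgery as a suitable endpoint. It does not touch the primary safety analysis, and it does not show that a false fall in surgery will occur.

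**What to change.** In SAP 6.2.2, for endpoints 1 to 4:

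1. State which rule applies to a subject who leaves before Month 6 or Month 12: partial total kept, or no value.
2. Add removals per patient-year of observation in the Safety population, overall and by HHI subgroup, with follow-up time tabulated. Assign removals in the 15-day post-Exit window to the exit assessment. Say that the rate reduces bias but does not remove it if leavers' rates differ. In the extreme example above it gives 440 removals over 90 patient-years, or 4.9 a year, against a true 5.6, still about 13% low.
3. Show removals up to Month 6 for subjects who left before Month 12 beside those who stayed, with numbers in each group.

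If half-year periods are shown side by side in subjects observed throughout, show removals of lesions identified at Baseline separately, because they front-load the first period.

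The change is SAP wording and about one extra table from data already collected. The downside is that the removal figure may look slightly less favourable.
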